7.3.4 FINAL STUDY VISIT

Week 52 Phase A End of Study (EOSa)

This study visit should occur on Day 365 with a window of -3 to + 7 days. Subjects should fast for 8 hours prior to this visit.

The following procedures and assessments will be performed at Week 52 (EOSa):

- Collection of AE and concomitant procedures/therapies/medication data
- Review of medical history
- Vital signs measurements (pulse rate, blood pressure, respiratory rate, and temperature)
- Physical examination, including knee examination of both knees
- Weight measurement
- Venipuncture and collection of samples for clinical laboratory tests and biomarker analysis
- Radiograph – bilateral in weight-bearing fixed flexion position, posterior-anterior (PA) view X-ray
- qCT of both knees
- DXA of the spine and hips

For subjects who consent to participate in Phase B, prior to study medication injection, the Investigator should evaluate the subject for suitability to receive the injection (refer to [Section 6.1.9](#)). The injection may occur up to two weeks later than the Week 52 (EOSa) visit to allow for resolution of any intercurrent illness (e.g., infection) prior to the injection. The subject should complete all other Week 52 (EOSa) assessments and return for an unscheduled visit and injection in the case that they are not able to receive the injection at the Week 52 (EOSa) visit. If the subject is determined to be suitable for injection, the subject will receive an intra-articular study medication injection (or placebo).

Note: The Week 52 (EOSa) WOMAC and Patient Global Assessment must be completed prior to the Week 52 (EOSa) study medication injection

7.3.5 EXTENSION PHASE (PHASE B)

Week 64 and Week 88

The Week 64 visit should occur on Day 449 (with a window of +7 days) and the Week 88 visit should occur on Day 617 (with a window of + 7 days). Subjects should fast for 8 hours prior to these visits.

The following procedures and assessments will be performed at these visits:

- Collection of AE and concomitant procedures/medication data
- Physical examination, including knee examination of both knees
- Vital signs measurements (pulse rate, blood pressure, respiratory rate, and temperature)
- Venipuncture and collection of samples for clinical laboratory tests and biomarker analysis
- qCT of both knees

Week 76

The Week 76 visit should occur on Day 533 (with a window of + 7 days). Subjects should fast for 8 hours prior to this visit. Prior to study medication injection, the Investigator should evaluate the subject for suitability to receive the injection (refer to [Section 6.1.9](#)). The injection may occur up to two weeks later than the Week 76 visit to allow for resolution of any intercurrent illness (e.g., infection) prior to the injection. The subject should complete all other Week 76 assessments and return for an unscheduled visit and injection in the case that they are not able to receive the injection at the Week 76 visit.

The following procedures and assessments will be performed at this visit:

- Collection of AE and concomitant procedures/medication data
- Physical examination, including knee examination of both knees
- Vital signs measurements (pulse rate, blood pressure, respiratory rate, and temperature)
- Weight measurement
- Venipuncture and collection of samples for clinical laboratory tests and biomarker analysis
- Radiograph – bilateral in weight-bearing fixed flexion position, posterior-anterior (PA) view X-ray
- qCT of both knees
- DXA of the spine and hips
- Intra-articular study medication injection (or placebo)

Note: The Week 76 WOMAC and Patient Global Assessment must be completed prior to the Week 76 study medication injection.

Week 104 Phase B End of Study (EOSb)

This final study visit should occur on Day 729 with a window of + 7 days. Subjects should fast for 8 hours prior to this visit.

The following procedures and assessments will be performed at Week 104 (EOSb):

- Collection of AE and concomitant procedures/therapies/medication data
- Review of medical history
- Vital signs measurements (pulse rate, blood pressure, respiratory rate, and temperature)
- Physical examination, including knee examination of both knees
- Weight measurement
- Venipuncture and collection of samples for clinical laboratory tests and biomarker analysis
- Radiograph – bilateral in weight-bearing fixed flexion position, posterior-anterior (PA) view X-ray
- qCT of both knees
- DXA of the spine and hips

7.3.6 EARLY TERMINATION VISIT

If possible, the following procedures and assessments should be performed within 14 days of subject premature withdrawal or termination. Subjects should fast for 8 hours prior to this visit.

- Collection of AE and concomitant procedures/therapies/medication data
- Review of medical history
- Vital signs measurements (pulse rate, blood pressure, respiratory rate, and temperature)
- Physical examination, including knee examination of both knees
- Weight measurement
- Venipuncture and collection of samples for clinical laboratory tests and biomarker analysis
- Radiograph – bilateral in weight-bearing fixed flexion position, posterior-anterior (PA) view X-ray
- qCT of both knees
- DXA of the spine and hips

Protocol SM04690-OA-06
Samumed, LLC

AM04V00
21 August 2020

7.3.7 SCHEDULE OF EVENTS TABLE

Procedure	Phase A											ET
	Screening Period ^a (Days -19 to -1)		Day 1 ^b	Week 4 (Day 29 +3 days)	Week 12 (Day 85 ±3 days)	Week 24 ^c (Day 169 +3 days)	Week 36 (Day 253 -3 to + 7 days)	Week 52 ^c (EOSa) (Day 365 -3 to +7 days)	Week 64 (Day 449 +7 days)	Week 76 ^c (Day 533 +7 days)	Week 88 (Day 617 +7 days)	
	Screening Visit 1 (Days -19 to -10)	Screening Visit 2 (Days -16 to -7)		Week 4 (Day 29 +3 days)	Week 12 (Day 85 ±3 days)	Week 24 ^c (Day 169 +3 days)	Week 36 (Day 253 -3 to + 7 days)	Week 52 ^c (EOSa) (Day 365 -3 to +7 days)	Week 64 (Day 449 +7 days)	Week 76 ^c (Day 533 +7 days)	Week 88 (Day 617 +7 days)	
Informed consent	X											
Inclusion & exclusion criteria	X		X									
Demographics	X											
Medical history	X		X					X ^d				X ^d
Current and prior procedures/medications	X		X									
Serum pregnancy test		X										
Urine pregnancy test			X ^e									
Urine drug test	X											
WPI & SS	X											
Radiograph	X					X		X		X		X
qCT		X			X	X	X	X	X	X	X	X
DXA		X				X		X		X		X
Physical examination	X		X	X	X	X	X	X	X	X	X	X
Knee examination	X		X	X	X	X	X	X	X	X	X	X
Selection of target knee	X											
Height	X											
Weight	X					X		X		X		X

Protocol SM04690-OA-06
Samumed, LLC

AM04V00
21 August 2020

Procedure	Phase A										Phase B				ET
	Screening Period ^a (Days -19 to -1)		Day 1 ^b	Week 4 (Day 29 +3 days)	Week 12 (Day 85 ±3 days)	Week 24 ^c (Day 169 +3 days)	Week 36 (Day 253 -3 to +7 days)	Week 52 ^c (EOSa) (Day 365 -3 to +7 days)	Week 64 (Day 449 +7 days)	Week 76 ^c (Day 533 +7 days)	Week 88 (Day 617 +7 days)	Week 104 (EOSb) (Day 729 +7 days)			
	Screening Visit 1 (Days -19 to -10)	Screening Visit 2 (Days -16 to -7)													
Vital signs	X		X	X	X	X	X	X	X	X	X	X	X	X	
Clinical laboratory sampling		X		X	X	X	X	X	X	X	X	X	X	X	
Biomarkers ^f		X		X	X	X	X	X	X	X	X	X	X	X	
Electronic diary and questionnaire training		X ^g (eDiary device provision & training)													
Pain NRS (Review)			X ^h												
WOMAC (Review)			X ⁱ												
Randomization			X												
Intra-articular injection			X			X		X		X	X				
AEs and concomitant procedures/medications			X	X	X	X	X	X	X	X	X	X	X	X	

^a The screening period is a minimum of 10 days and a maximum of 19 days and includes Screening Visit 1 and Screening Visit 2; Screening Visit 2 should occur at least 3 days after Screening Visit 1, at least 7 days prior to Day 1, and after confirmation of eligible radiograph and urine drug test report results.

^b At Day 1, all procedures should be performed prior to study medication injection except for collection of AE and concomitant procedures/medication data.

^c At Week 24, 52 (EOSa), and 76, all procedures should be performed prior to study medication injection.

^d Review medical history to capture End Date(s), if applicable, of any ongoing medical history(ies) collected at screening.

^e Urine pregnancy test on Day 1 will only be performed on female subjects of childbearing potential.

^f Concentrations of bone and cartilage biomarkers are analyzed in the serum.

^g Electronic diary devices will be provided to subjects at Screening Visit 2; subject electronic diary and questionnaire training will be conducted at Screening Visit 2.

^h Electronic diary compliance for daily pain NRS over the screening period will be reviewed at Day 1 prior to randomization to determine subject eligibility.

ⁱ WOMAC questionnaire will be reviewed at Day 1 prior to randomization to determine subject eligibility.

7.3.8 SCHEDULE OF ELECTRONIC DIARY AND QUESTIONNAIRE COMPLETION TABLE

	Monthly WOMAC and Patient Global Assessment	Daily pain NRS
Study Week/Day (Study Visits are denoted with grey shading.)	WOMAC and Patient Global Assessment will be completed by subjects 5 days after Screening Visit 2 (or up until the day before the Day 1 visit) and monthly in the evening (between 5:00 pm and 11:59 pm) remotely on their electronic devices. Monthly questionnaires should be performed within a window of \pm 3 days as outlined below; ranges shown are inclusive.	Pain NRS should be completed daily starting after Screening Visit 2. Subjects will complete the diary in the evening (between 5:00 pm and 11:59 pm) remotely on their electronic devices. Diary completion should occur every day including on study visit days.
Screening Visit 1		
Screening Visit 2		
5 days after Screening Visit 2	Baseline WOMAC and Patient Global Assessment questionnaires (or up until the day before the Day 1 visit)	Complete daily starting on the same day of Screening Visit 2 (after the visit); pain NRS assessments are to be completed for each knee.
Day 1		Starting on the same day of Day 1 (after the visit), pain NRS assessments are to be completed for the target knee only. Complete daily.
Week 4 (Day 29)	Complete between Day 26 and 32	
Week 8 (Day 57)	Complete between Day 54 and 60	
Week 12 (Day 85)	Complete between Day 82 and 88	
Week 16 (Day 113)	Complete between Day 110 and 116	
Week 20 (Day 141)	Complete between Day 138 and 144	
Week 24 (Day 169)*	Complete between Day 166 and 172	
Week 28 (Day 197)	Complete between Day 194 and 200	
Week 32 (Day 225)	Complete between Day 222 and 228	
Week 36 (Day 253)	Complete between Day 250 and 256	
Week 40 (Day 281)	Complete between Day 278 and 284	
Week 44 (Day 309)	Complete between Day 306 and 312	
Week 48 (Day 337)	Complete between Day 334 and 340	
Week 52 (Day 365)*	Complete between Day 362 and 368	
Week 56 (Day 393)	Complete between Day 390 and 396	
Week 60 (Day 421)	Complete between Day 418 and 424	
Week 64 (Day 449)	Complete between Day 446 and 452	

	Monthly WOMAC and Patient Global Assessment	Daily pain NRS
Week 68 (Day 477)	Complete between Day 474 and 480	
Week 72 (Day 505)	Complete between Day 502 and 508	
Week 76 (Day 533)*	Complete between Day 530 and 536	
Week 80 (Day 561)	Complete between Day 558 and 564	
Week 84 (Day 589)	Complete between Day 586 and 592	
Week 88 (Day 617)	Complete between Day 614 and 620	
Week 92 (Day 645)	Complete between Day 642 and 648	
Week 96 (Day 673)	Complete between Day 670 and 676	
Week 100 (Day 701)	Complete between Day 698 and 704	
Week 104 (Day 729)	Complete between Day 726 and 732	

***Note:** At Weeks 24, 52 (EOSa), and 76, the WOMAC and Patient Global Assessment must be completed prior to the Week 24, 52 (EOSa), and 76 study medication injections, respectively.

7.4 JUSTIFICATION FOR SENSITIVE PROCEDURES

Not applicable for this study.

7.5 CONCOMITANT MEDICATIONS, TREATMENTS, AND PROCEDURES

Details regarding the name, indication, route of administration, dose, and frequency of all medications taken within 30 days prior to Screening Visit 1 through the subject's last visit will be recorded in the "Prior and Concomitant Medications" eCRF. "All medications" should include prescription, over the counter, supplements, as well as herbal or alternative medications.

Procedures or non-drug therapies that are ongoing, new, or modified at or after the Screening Visits must be recorded on the "Procedures and Non-Drug Therapies" page of the eCRF.

Any new or modified concomitant therapy must be considered to determine if it is related to an AE.

7.5.1 PRECAUTIONARY MEDICATIONS, TREATMENTS, AND PROCEDURES

Not applicable to this study.

7.6 PROHIBITED MEDICATIONS, TREATMENTS, AND PROCEDURES

Prohibited Concomitant Medications and Procedures:

- Any intra-articular injection, including glucocorticoids, hyaluronic acid derivatives, PRP, stem cell therapies, or other agents with therapeutic intent, into either knee is prohibited while the subject is on study; intra-articular injection of glucocorticoids, hyaluronic acid derivatives, PRP, stem cells, or other therapeutic agents into joints other than the knee is allowed.
- The following medications are prohibited while the subject is on study:

- Opioids; short-term use of opioids as part of anesthesia or procedural sedation during the study period is permitted
- Centrally acting analgesics (e.g., duloxetine) (refer to [Appendix 1](#))
- Other anticonvulsants not listed in [Appendix 1](#) are also prohibited unless used for seizure or migraine prophylaxis
- Systemic glucocorticoids greater than 10 mg of prednisone per day or the equivalent
- Drugs screened to assess eligibility, unless clinically indicated and allowed by the protocol: amphetamine, buprenorphine, cocaine, methadone, opiates, PCP, propoxyphene, barbiturates, benzodiazepine, methaqualone, and tricyclic antidepressants
- Electrotherapy (refer to [Appendix 1](#)), acupuncture, and/or chiropractic treatments for knee OA are prohibited while the subject is on study.
- Any new formalized (i.e., prescribed by a medical professional) physical therapy exercise programs for knee OA are prohibited while the subject is on study; continuation of formalized physical therapy exercise programs that are already in progress at the time of screening are allowed.
- Elective surgery, including arthroscopy, is prohibited while the subject is on the study. Non-surgical invasive procedures conducted for a diagnostic or therapeutic purpose that are scheduled during the study period are not prohibited. Examples include, but are not limited to: endoscopy, colonoscopy, bronchoscopy, cystoscopy, radiologic procedures such as coronary artery catheterization with or without intervention, and non-surgical cosmetic procedures such as Botox or other cosmetic injections.
- Subjects are prohibited from participating in any other clinical research trial that includes the receipt of an investigational product or any experimental therapeutic procedure. Subjects are also prohibited from participating in any observational research trial related to OA while on study.

The Investigator should notify the Samumed Medical Monitor immediately if any prohibited therapies are required to ensure subject safety.

7.7 PROPHYLACTIC MEDICATIONS, TREATMENTS, AND PROCEDURES

Not applicable to this study.

7.8 RESCUE MEDICATIONS, TREATMENTS, AND PROCEDURES

Not applicable to this study.

7.9 PARTICIPANT ACCESS TO STUDY AGENT AT STUDY CLOSURE

Not applicable to this study.

8. ASSESSMENT OF SAFETY

8.1 SPECIFICATION OF SAFETY PARAMETERS

Safety assessments include physical examinations, vital signs, clinical laboratory tests, collection of AEs, SAEs, and concomitant medications, and general medical evaluations.

8.1.1 DEFINITION OF ADVERSE EVENTS (AE)

AEs in the eCRF will be classified according to the most recent US FDA definitions and in a manner consistent with ICH-GCP guidelines. As such the following definitions will be used:

An AE is any unfavorable and unintended sign, symptom, or disease temporally associated with the use of an investigational (medicinal) product (IP) or other protocol-imposed intervention, regardless of attribution. An AE may include intercurrent illnesses or injuries that represent an exacerbation (increase in frequency, severity, or specificity) of preexisting conditions (e.g., worsening of asthma).

Whenever possible, it is preferable to record a diagnosis as the AE term rather than a series of symptoms relating to a diagnosis. Fluctuations of pre-existing conditions, including the disease under study that does not represent a clinically significant exacerbation or worsening, need not be considered AEs. In order to classify AEs and diseases, preferred terms will be assigned by the Sponsor to the original terms entered on the eCRF, using the Medical Dictionary for Regulatory Activities (MedDRA).

In this protocol, signs and symptoms of exacerbation or worsening of target knee OA will be captured in the context of efficacy assessments and recorded on specific pages of the eCRF or electronic diary. Anticipated fluctuations or anticipated deterioration (in the opinion of the Investigator) of the underlying disease (target knee OA) will not be considered as AEs nor captured on the AE page of the eCRF.

8.1.2 DEFINITION OF SERIOUS ADVERSE EVENTS (SAE)

According to the ICH Guidelines for Good Clinical Practice (E6), an SAE is any untoward medical occurrence during the course of a clinical investigation that is characterized by 1 or more of the following:

- Results in death
- Is life threatening
- Requires inpatient hospitalization or prolongation of existing hospitalization
- Results in persistent or significant disability/incapacity
- Is a congenital anomaly/birth defect
- Is an important medical event, defined as an event that does not fit one of the other outcomes, but may jeopardize the subject and may require medical or surgical intervention (treatment) to prevent one of the other outcomes. Examples include allergic bronchospasm (a serious problem with breathing) requiring treatment in an emergency room, serious blood dyscrasias (blood disorders), or seizure/convulsion that does not result in hospitalization. The development of drug dependence or drug

abuse would be other examples of important medical events.

“Inpatient hospitalization” is clarified as hospitalization lasting ≥ 24 hours. Admission to the hospital or prolongation of hospitalization qualifies as an SAE only if it is the result of an AE.

All SAE information must be recorded on the SAE form approved by the Sponsor. Additional follow-up information (e.g., test results, autopsy, and discharge summary) may be requested to supplement the SAE report form and can be attached as de-identified records.

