7. STUDY PROCEDURES AND SCHEDULE

7.1 STUDY PROCEDURES/EVALUATIONS

7.1.1 STUDY SPECIFIC PROCEDURES

Collection of Adverse Events Data

Data regarding AEs will be collected in this study. AEs are events that occur during the course of the study that are not present prior to Day 1 study medication injection, or, if present at the time of study medication injection, have worsened in severity during the course of the study. AEs will be assessed at each study visit from the time of study medication injection on study visit Day 1 through the subject's last study visit.

Each subject will be observed and queried by the Investigator or the Investigator's designee at each study visit for any continuing AEs or new AEs since the previous visit. The subject may be asked to return to the site for an unscheduled visit if an AE occurs between study visits, and if, in the opinion of the Investigator, the AE requires a study visit for full evaluation. Any AE reported by the subject or noted by the Investigator or the Investigator's designee will be recorded within the eCRF. The following information will be recorded for each AE: description of the event, date of onset and resolution, etiology, and severity as assessed by the Investigator according to the Clinical Data Interchange Standards Consortium (CDISC) Severity/Intensity Scale for Adverse Events (AESEV) ([Table 1](#)), causal relationship to study medication, outcome, and any treatment given.

In this protocol, signs and symptoms of exacerbation or worsening of target knee OA will be captured in the context of efficacy assessments and recorded on specific pages of the eCRF.

Anticipated fluctuations or anticipated deterioration (in the opinion of the Investigator) of the underlying disease (target knee OA) will not be considered as AEs nor captured on the AE page of the eCRF.

Whenever possible, it is preferable to record a diagnosis as the AE term rather than a series of symptoms relating to a diagnosis. Fluctuations of pre-existing conditions, including the disease under study, that do not represent a clinically significant exacerbation or worsening, need not be considered AEs.

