8.2 General Safety Assessments

8.2.1 Adverse Events

An AE is any unfavorable and unintended sign, symptom, or disease temporally associated with the use of an IP or other protocol-imposed intervention, regardless of attribution. Signs and symptoms of exacerbation or worsening of target knee OA were captured in the context of efficacy assessments. Anticipated fluctuations or anticipated deterioration (in the opinion of the Investigator) of the underlying disease (target knee OA) were not considered as AEs.

Severity was assessed utilizing the CDISC AESEV, which classifies AEs as mild, moderate, or severe. For analysis, relationship will be dichotomized into Unrelated (combining Not Related and Unlikely Related) and Related (combining Possibly Related and Probably Related).

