14.1 Concomitant Medications

The World Health Organization Drug Dictionary (WHODD) will be used to classify prior and concomitant medications by Anatomical Main Group (Anatomical Therapeutic Chemical, ATC, Level 1), Therapeutic Subgroup (ATC Level 2), and preferred term. Prior and concomitant medication usage will be summarized by the number and percentage of subjects receiving each medication by treatment group.

The subgroup of medications initiated after Week 52 injection will be summarized in the same manner. If a medication start date is incomplete, it will be imputed with the latest possible date to increase the likelihood it is included in the table of medications initiated after first exposure. For example, medication start dates of “2019” and “2020-02” would be imputed to “2019-12-31” and “2020-02-29”, respectively.

Subject-level listings containing prior and concomitant medications (WHODD coding), and procedures/non-drug therapies (MedDRA coding) will be provided and will display the dates as they were entered (not the imputed version described above).

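### Inpatient surgery on the injected knee can be classed as neither an AE nor, under the hospitalization criterion, an SAE, and no planned table counts it by arm

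*Protocol*

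**What the plan says.** Three statements bear on the classification.

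- **SAE rule, Protocol 8.1.2.** Inpatient hospitalization is one of six seriousness criteria. It is then narrowed: "Admission to the hospital or prolongation of hospitalization qualifies as an SAE only if it is the result of an AE".
- **AE exclusion, Protocol 8.1.1.** Changes in the target knee that the Investigator regards as anticipated, "of the underlying disease (target knee OA) will not be considered as AEs nor captured on the AE page of the eCRF". Protocol 7.1.1 repeats this and adds that "signs and symptoms of exacerbation or worsening of target knee OA will be captured in the context of efficacy assessments". SAP 8.2.1 carries it into the analysis definition: "Anticipated fluctuations or anticipated deterioration (in the opinion of the Investigator) of the underlying disease (target knee OA) were not considered as AEs". None of these places sets a severity limit or makes an exception for surgery or admission.
- **General rule on pre-existing conditions, Protocol 8.1.1 and 7.1.1.** Here the exemption is narrower. It covers only a fluctuation "that does not represent a clinically significant exacerbation or worsening, need not be considered AEs".

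Protocol 7.5 requires procedures to be entered on the Procedures and Non-Drug Therapies eCRF page. For these, SAP 14.1 plans only subject-level listings: "procedures/non-drug therapies (MedDRA coding) will be provided". Protocol 8.4.4 defines no events of special interest.

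**The concern.** The primary objective is the safety and tolerability of repeated injections into one joint. The AE exclusion applies only to that joint and depends on one judgement, whether the deterioration was anticipated. The admission sentence in 8.1.2 then passes that judgement on to the SAE classification. So an operation on the treated knee can miss the AE and SAE tables, while the same operation on the untreated knee would be counted.

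The target-knee-related AE and SAE table in SAP 10.1 is the natural place to look for such events. It is built from AE records and inherits the gap.

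**Working it through.** The plan states no figure on this point, so there is none to reproduce. The check applies the rules to one record and then searches for text that closes the gap.

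**1. One record, two knees.** Suppose that at Week 60 a subject is admitted for three days for replacement of a knee whose OA has worsened, and the Investigator judges the worsening anticipated. Three days exceeds the 24-hour threshold for inpatient hospitalization in Protocol 8.1.2.

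| Step | Injected knee | Other knee |
|---|---|---|
| Target-knee exclusion (8.1.1) | Applies: not an AE | Does not apply |
| General rule (8.1.1) | Points to an AE if clinically significant | Clinically significant, so an AE |
| Admission results from an AE? (8.1.2) | No, if the exclusion prevails | Yes |
| SAE by hospitalization criterion | No, if the exclusion prevails | Yes |

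**2. Text that pulls the other way.**
- The general rule in 8.1.1 and 7.1.1 exempts only worsening that is not clinically significant, and it names the disease under study.
- The knee-examination paragraph in 7.1.1 makes clinically significant findings in either knee after injection reportable as AEs.
- Protocol 8.1.2 lists persistent or significant disability and important medical events as separate criteria, and defines an SAE as an untoward medical occurrence.

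None of these says that it overrides the target-knee exclusion, and the exclusion does not say that it overrides them.

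**3. Can the event happen under observation?** Yes. Elective surgery is prohibited (Protocol 7.6), but SAP 4.4.2 says that use of a prohibited therapy did not automatically discontinue a subject. Subjects withdrawn from injections for safety, or judged unsuitable for one, continue their visits (Protocol 5.5.2 and 6.1.9).

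**4. Where the operation would still appear.**
- Procedures and Non-Drug Therapies page: listed by subject (SAP 14.1).
- Protocol deviations, if it was a prohibited procedure: listed by subject. If major and in Phase B, it is also summarized by site and category (SAP 9.2), with no breakdown by arm stated.
- Disposition, if the subject discontinues: counted by treatment group with the reason (SAP 9.1), but not as knee surgery.
- Efficacy: Pain NRS, WOMAC, Patient Global Assessment and mJSW (SAP 12). None of these counts surgery.

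No planned table gives target-knee surgery by arm.

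**5. Size.** One event among n subjects in an arm is 100/n percentage points. At the planned n = 50, 100/50 = 2 points. The number of events is not in the documents. For an assumed one, two or three subjects in one arm, the omission is 1/50 = 2%, 2/50 = 4% or 3/50 = 6% of that arm. The Phase B safety set (SASB, SAP 7.7) includes only subjects injected in Phase B, so its n may be below 50 and each event would then exceed 2 points.

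**The case against.** The strongest reply is that deterioration leading to inpatient surgery is clinically significant almost by definition, so the general rule and the knee-examination paragraph already make it an AE. It is also not obviously anticipated in this population. Kellgren-Lawrence Stage 4 target knees and subjects with scheduled surgery are excluded at entry (Protocol 5.2, criteria 7 and 11), and elective surgery is prohibited on study. This stands as a reason to expect that many Investigators would report the event. It does not settle the rule. The target-knee exclusion is the more specific provision, is worded as mandatory, and names deterioration as well as fluctuation, so a site could reasonably follow it.

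The other SAE criteria also stand in part. The admission sentence restricts only the hospitalization route. Disability could still apply. The important-medical-event route is open to argument, because it is meant for events that fit none of the other outcomes.

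A reader might infer more than the text supports:

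- *That such an operation will always count as zero AEs and zero SAEs.* The gap opens only when the Investigator judges the deterioration anticipated and lets that rule prevail. Joint infection or unanticipated worsening is not covered by the exclusion.
- *That the operation disappears from the data.* It remains traceable through the sources in step 4.
- *That an excess on SM04690 would be hidden.* That would need every case to be judged anticipated. The rule is the same in both arms, and Investigators who assess subjects are blinded. An excess could be understated, but the documents do not show that it would be.
- *That a specific distortion of SAE rates can be stated.* Without a surgery rate, any pair of arm-level percentages is assumed.

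**Conclusion.** The point holds as an unresolved conflict of definitions together with a missing table. Following Protocol 8.1.1 and 8.1.2 as written can leave an inpatient operation on the injected knee outside AE classification and outside the hospitalization route to an SAE. No planned by-arm summary recovers it. The effect is 2 percentage points of an arm per event at 50 per arm, possibly more in Phase B; the number of events is unknown.

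Two assumptions matter: that some Investigators treat the target-knee exclusion as controlling, and that such operations occur during follow-up. The statement about planned tables rests on the protocol and the Phase B SAP. The separate Phase A SAP was not available, although SAP 10.1 covers AEs for the whole study as well as for Phase B. This is an inexpensive correction worth making, not evidence that the safety comparison is biased.

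**What to change.** 1. **Reconcile the reporting rule** across Protocol 7.1.1 (AE collection and knee examination), 8.1.1 and 8.1.2, and align SAP 8.2.1. A clinically significant worsening of the target knee that leads to admission or surgery should be reported as an AE, whether or not it was anticipated. It should be an SAE where a seriousness criterion is met. Recording it by diagnosis keeps to the protocol's stated preference.
2. **Add to SAP 10.1** the number and percent of subjects by arm with target-knee surgery, for the whole study (SAS) and for Phase B (SASB). Take it from the Procedures and Non-Drug Therapies page as well as the AE page.

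The second change matters more. The SAP describes conduct largely in the past tense, so new protocol wording may come too late to alter what was captured, whereas the table uses a page already in the eCRF.

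The cost is a short clarification and one table row. A few disease-related operations would enter the safety tables in both arms. The procedures page records procedures, not admissions, so non-surgical admissions left out before the change may not be recoverable from it.
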